### Field Observations

We will conduct 10 field observations of intervention activities, such as the wellness visits and the conduct of viral load testing. Observations will be conducted by trained RAs and recorded as field notes on a structured template that organizes narrative descriptions by topic.

### **Qualitative data analysis**

The goal of the qualitative analysis is to produce an in-depth analysis of acceptability of intervention components from the points of view of male and female participants. The construct of acceptability is broadly defined to target not only participants' feelings and attitudes toward the intervention, but also allow for the interpretation of their broader experiences with intervention components. The qualitative analysis will address "how" and "why" questions about intervention dynamics to inform future dissemination and implementation.

All qualitative data will be analyzed using an inductive content analysis approach. First, we will review the data to derive a general sense of content relevant to the construct of acceptability. Following the initial review, a subset of the data will be re-reviewed to descriptively label relevant sections of text (open-coding). Descriptive labels will be defined, illustrated, and assembled into a codebook to guide directed coding, in which the codebook is used to code the entire data set. The directly coded data will be iteratively grouped and regrouped to identify relevant emergent content. Results will be rendered as conceptual categories consisting of labels, descriptive text, and illustrative quotes, and linked through grounded interpretation.

### **Sample size considerations**

Aim 1: The primary analysis will be an intent to treat comparison by randomization arms of the primary outcome of the proportion of women whose male partners who test for HIV, comparing Arm 1 and 2 combined to Arms 3 and 4 combined.

Aim 2: The primary analysis will assess proportion of women who are virally suppressed at 6 month post-partum by randomization arms comparing Arm 1 and 3 combined to Arms 2 and 4 combined.

### **Power to detect a difference in HIV testing uptake in male partners with 200 women**

Power is 80% to detect an increase in HIV testing of 20-22% in the male partner testing, as shown in Table 4, assuming:

- the test uptake in the standard of care arm is 20-30% (20% observed in MU-JHU's program and anticipating some increase with new MOH program to offer HIVST in ANC programs)
- test uptake in intervention arm is 42-50% (assuming that the broader services offered in the intervention arm through wellness visits will increase HIV testing by 20-22%)
- Power is based on a log-rank test for time from randomization of a pregnant woman to her male partner receiving HIV test in the clinic

### **Power to detect a difference in viral suppression in female partners with 200 women**

Assuming 60-80% of pregnant women in Kingasa will be virally suppressed at 6 months post-partum in the standard of care arm (which is lower than Obumu due to the impact of COVID-19 on women’s ability to leave home for ART refills and adherence among women who have not disclosed), we have 80% power with a two-sided alpha of 0.05 to detect an 13-18% increase in viral suppression as a result of the POC VL test (Table 4). The primary analysis for effectiveness of male testing will compare Arms 1 and 2 combined compared to Arms 3 and 4 combined, the primary analysis for effectiveness of POC VL and targeted adherence will compare the two groups with and without POC VL (i.e. Arms 1 and 3 combined compared to Arms 2 and 4 combined). An intention to treat approach will be used.

Aim 1:	Probability of outcome in SOC conditions	Outcome change that can be detected with 80% power	Aim 2:	Probability of outcome in SOC conditions	Outcome change that can be detected with 80% power
Outcome: Male Partner tested for HIV (N = 200)	20%	22%	Outcome: VS of the women at 6 months post-partum	60%	18%
	25%	21%		70%	16%
	30%	20%		80%	13%

The analysis for HIV testing in the male partner will use Kaplan Meier methods to estimate the proportion of women who have their male partner tested during the study, using time from the women’s enrollment until her partner tests. The proportion will be assessed at 6 and 12 months as the survival curve estimate at the end of the visit window. A log-rank test will be used to evaluate the difference between arms in proportion tested. The analysis for VS at 6 months post-partum will use logistic regression to assess the odds of VS at the 6-month post-partum visit.

Outcome measurements

Aim 1: The outcome for Aim 1 is the proportion of men who come to the ANC clinic to test for HIV in the intervention arm compared to those randomized to the control arm, including whether they initially used a HIVST before coming to the clinic.

Aim 2: The outcome for Aim 2 is viral suppression at 6 months postpartum, assessed at this visit.

Aim 3: The primary outcome is the proportion of HIV-negative male partners who initiate PrEP and HIV-positive men who initiate ART within 6 months across both arms. The secondary outcome will evaluate the proportions who initiate PrEP and ART by arm. The outcomes are engagement in care, defined as: 1) PrEP initiation among HIV negative men or 2) ART initiation among HIV positive men. PrEP use will be measured by pharmacy records where men are dispensed PrEP (e.g. at Kitebi clinic or IDI Kasangati), and self-report through a validated questionnaire. ART initiation will be assessed through pharmacy records.

Capture of cohort clinical data

Data on male partner HIV testing and female partner ART use and viral load will be obtained from case report forms. Clinic and pharmacy records will be used to document PrEP prescriptions, abstracted in real time from pharmacy records to paper-based case report forms and entered into an electronic database. Automated legal range checks will be programmed to reduce data entry errors and internal quality control reports will be run monthly.

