### POC HIV Viral Load

Based on our preliminary analysis of women in Obumu who have had a 6 and/or 12-month post-partum visit, 24% and 34%, respectively, have not had a viral load recorded (compared to 98% at enrollment). Among postpartum who have had a viral load obtained, 20-22% had detectable viral load. Missing viral

loads and detectable viral load among postpartum women, combined with not receiving their results until their next postpartum visit indicates that a substantial proportion of postpartum women living with HIV are not receiving the benefit of viral load monitoring and prompt ART adherence counseling. Additionally, DNA-PCR coverage for early infant diagnosis (EID) in Uganda is suboptimal; only 64% of HIV exposed infants (HEI) received an initial DNA PCR test delivery, < 55% of HEI receive a virological test within 2 months of birth, and only 28% receive their final rapid test at 18 months of age (89).

The feasibility of POC VL with Xpert HIV-1 VL at the time of delivery combined with neonatal diagnosis EID using the Xpert HIV-1 EID has been demonstrated in South Africa (90). Approximately 75% of mothers and newborns received the maternal POC VL and EID prior to discharge (91). A field evaluation of POC EID for neonatal diagnosis in South Africa showed good performance, improved rates of results returned to mothers (96% compared to 89% of lab-based EID), and reduced time to ART initiation for infected neonates (5 days earlier for infants diagnosed with the Xpert HIV-1 EID). Additional evaluation is needed in non-tertiary obstetric units and health centers in terms of feasibility of introducing POC maternal VL and EID in terms of implementation aspects, coverage, turn-around time, and results return before women are discharged after delivery.

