## **STUDY METHODS**

### *Overall design*

This is a randomized factorial trial to assess two strategies; one to increase HIV testing and engagement  
Kingasa Study Protocol

in care among male partners of pregnant women, and the second to improving ART continuation and adherence among the HIV-positive pregnant women. The overall goal is to evaluate the impact of innovative strategies to increase male partner HIV testing, and engagement in HIV care and prevention among men and their pregnant partners, through ANC services provided to HIV- positive women.

We will recruit HIV-positive women with a partner of unknown HIV status through PMTCT B+ programs at Kitebi Health Center III in Kampala. Women will be randomized 1:1:1:1 to

- Arm 1: Women will be provided the standard of care invitation letter for male partners for fast-track visit for HIV testing and laboratory HIV testing at enrollment and every 6 months until 6 months postpartum,
- Arm 2: Women will be provided the standard of care invitation letter for male partners for fast-track visit for HIV testing and POC VL tests for women at enrollment, delivery, and 6 months post-partum;
- Arm 3: Women will be provided an invitation letter for male partners for wellness visits and laboratory-based HIV VL testing for women at enrollment, delivery, and 6 months post-partum;
- Arm 4: Women will be provided an invitation letter for male partners invitation letter for male partners for wellness visits and POC viral load testing for women at enrollment, delivery, and 6 months post-partum.

Women who are randomized to receive POC VL will receive same day ART adherence counseling and those randomized to receive lab based VL will receive VL results at their next visit with ART adherence counseling based on their VL results.

Male partners of women who are randomized to the wellness visit will receive a phone call from a male counselor after HIV testing to encourage linkage to care and prevention, depending on HIV status.

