Brief study questionnaires will be administered will occur at the PMTCT visits to avoid separate study-specific visits. Postnatal care and infant immunization visits will follow the routine maternal and child health (MCH) schedule. Viral load (VL) monitoring will include POC VL testing at enrollment, delivery, and every 6 months until M6 post-partum for women randomized to the intervention arm, and laboratory HIV RNA testing at enrollment, and every 6 months until M6 post-partum for women randomized to the control arm. Blood samples will be batch-tested at collaborating laboratories. Women will be asked about interruptions in ART use. If the mother is stable on ART with good adherence and undetectable VL, post-partum visits will be scheduled for week 6, and months 3 and 6. During these clinic visits, women will complete interviewer-administered surveys to collect data on behavioral factors that could mediate women's post-partum ART use. Women in the intervention arm will be provided their viral load results at that visit, and in the control arm will receive their viral load results at their next visit, in addition to counseling about the relationship between adherence, viral load and transmission risk.

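### Table 4, Aim 1: the detectable differences of 22/21/20 points run in the wrong direction and fit no single sample size, so power for partner testing is misreported, though not too low at N = 200

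*Protocol*

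**What the plan says.** Allocation is equal across the four arms ("Women will be randomized 1:1:1:1 to", Overall design). Each factorial comparison therefore sets 100 women against 100.

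**Aim 1.** The section on power for male partner testing states: "Power is 80% to detect an increase in HIV testing of 20-22% in the male partner testing". It takes standard-of-care uptake as 20-30% and adds that "test uptake in intervention arm is 42-50"%. The basis is given as "Power is based on a log-rank test for time from randomization of a pregnant woman" to her partner's test at the clinic. Table 4, in the next section, has the row "Outcome: Male Partner tested for HIV (N = 200") with three pairs: 20% and 22 points, 25% and 21 points, 30% and 20 points. The intervention rates are therefore 42%, 46% and 50%. No alpha is given for this aim.

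**Aim 2.** The text says "we have 80% power with a two-sided alpha of 0.05 to detect an 13-18% increase in viral suppression". Table 4 gives 18, 16 and 13 points at standard-of-care suppression of 60%, 70% and 80%.

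**The concern.** With sample size, power and alpha fixed, the detectable absolute difference depends only on the control rate. Between 20% and 30%, with the intervention rate at or below 50%, binomial variance increases with the rate, so a larger difference is needed as control uptake rises. The log-rank formulas behave in the same way over this range. The Aim 1 column does the opposite.

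This is a stated power result for a primary endpoint, and it appears in both the table and the text. A reader who tries to verify the trial's size from it cannot do so, because each row implies a different number of women.

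**Working it through.** **Inputs.** n = 100 per group, from N = 200 and equal allocation. Power 80% (z = 0.842). Pairs 20→42, 25→46 and 30→50, from Table 4. Two-sided alpha 0.05 (z = 1.960), stated for Aim 2 and assumed for Aim 1.

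**Formulas** (n per group):
- Two proportions, pooled: n = [1.960·√(2p̄(1−p̄)) + 0.842·√(p₁(1−p₁) + p₂(1−p₂))]² / (p₂−p₁)²
- Log-rank: HR = ln(1−p₂)/ln(1−p₁), total events = n(p₁+p₂)
- Schoenfeld events: 4(1.960+0.842)²/(ln HR)² = 31.4/(ln HR)²
- Freedman events: (1.960+0.842)²·[(HR+1)/(HR−1)]² = 7.85·[(HR+1)/(HR−1)]²

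**Step 1: sample size implied by each printed row.** For 20→42, HR = ln 0.58/ln 0.80 = 2.441 and ln HR = 0.8925. Schoenfeld events are 31.4/0.7965 = 39.4, so n = 39.4/0.62 = 63.6. For 30→50, HR = ln 0.50/ln 0.70 = 1.943 and ln HR = 0.6644. Events are 71.1, so n = 71.1/0.80 = 88.9. In full, rounded to the nearest woman:

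| Pair | Schoenfeld | Freedman | Two proportions |
|---|---|---|---|
| 20→42 | 64 | 72 | 68 |
| 25→46 | 76 | 84 | 80 |
| 30→50 | 89 | 96 | 93 |

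The rows do not share an n. A search over every n from 40 to 160 per group at 0.05 finds none whose detectable differences round to 22/21/20 under any of the three formulas.

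**Step 2: does the unstated alpha explain it?** No. The implied n rises from row to row at every two-sided alpha tried from 0.005 to 0.20. By two proportions it is 116/137/158 at 0.005, 83/97/113 at 0.025 and 39/46/53 at 0.20.

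**Step 3: detectable difference at 100 per group** (80% power, two-sided 0.05), in points:

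| Control uptake | Printed | Schoenfeld | Freedman | Two proportions |
|---|---|---|---|---|
| 20% | 22 | 17.4 | 18.2 | 17.9 |
| 25% | 21 | 18.3 | 19.0 | 18.7 |
| 30% | 20 | 18.8 | 19.5 | 19.3 |

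Adding a continuity correction to two proportions gives 18.9/19.8/20.3, which also rises. Only the 30% row is near its printed value.

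**Step 4: power of the printed differences at 100 per group.** Schoenfeld: power = Φ(√events·ln HR/2 − 1.960). For 20→42 this is Φ(√62 × 0.8925/2 − 1.960) = Φ(1.55) = 94%. The three rows have power 94/89/84% (Schoenfeld), 91/87/82% (Freedman) and 93/88/83% (two proportions).

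**Step 5: Aim 2.** The pooled formula at 100 per group gives 18.2/16.3/13.4, which rounds to the printed 18/16/13. It still does so at 98 per group (18.4/16.4/13.5, the last being 13.49 before rounding). At the rounded values, power with 100 per group is 79/78/77%.

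**The case against.** The strongest reply is that nothing follows from the error. At the printed N of 200 and two-sided 0.05, every printed row has more than 80% power by both log-rank formulas and by pooled two proportions. The protocol understates its power; it does not promise too much. No participant number, analysis or conclusion changes. All of that stands, and it limits the point to a correction of reporting. It does not make the column right: a protocol that states a power result should state one that can be reproduced.

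Three stronger readings are tempting, and the document does not support them.

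- **A reader might infer that Aim 1 is underpowered.** It is not at 100 per group with complete follow-up. The continuity-corrected formula would need 103 per group in the 30% row, but the protocol names the log-rank test.
- **A reader might infer that the column was computed for about 80 women per group and printed in reverse.** The order 20/21/22 would fit 73 to 83 per group at 0.05, depending on the formula. But the table states N = 200, and the text's 42-50% follows the printed order. In a log-rank analysis a woman lost early is censored, not removed. The cause cannot be settled from the protocol.
- **A reader might infer that the Aim 2 figures are wrong or hold only with all 200 women measured.** They reproduce, and they survive rounding at 98 per group. In the previous study, "24% and 34%, respectively, have not had a viral load recorded (compared to 98% at enrollment") at the 6- and 12-month post-partum visits. That is another study's rate. Here the month-6 test is scheduled in both groups, including "laboratory HIV RNA testing at enrollment, and every 6 months until M6 post-partum for women randomized to the control arm". How missing results are handled may also be left to the analysis plan; counting them as unsuppressed would keep all 200 in the denominator, though the protocol states no such rule.

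**Conclusion.** The Aim 1 column of Table 4, and the matching ranges in the Aim 1 power text, are wrong as written. The direction is wrong under every formula and alpha tried. The size depends on the assumed two-sided 0.05 and on complete follow-up at 100 per group. On that basis the printed differences are too large by about 4 to 5 points in the 20% row (22 against 17.4-18.2) and by about 0.5 to 1 point in the 30% row (20 against 18.8-19.5). The error is conservative.

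Aim 2 contains no arithmetic error. Its figures need a 6-month viral load from nearly all women, about 98 per group, and the sample-size text makes no allowance for fewer. If the previous study's 24% applied to both groups (76 per group), the detectable differences would be 20.6/18.3/14.9. That rate is an assumption for this trial, not a forecast.

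**What to change.** 1. State the alpha and the log-rank formula used for Aim 1.
2. Recompute the Aim 1 column at N = 200. Rounded up so that no row falls below 80% power, it is 18/19/19 by Schoenfeld (power 83/83/81%) or 19/20/20 by Freedman (power 83/83/82%).
3. Align the Aim 1 power text. By Schoenfeld the increase is 18-19 points and intervention uptake 38-49% (20+18 to 30+19). By Freedman they are 19-20 points and 39-50% (20+19 to 30+20).
4. If a smaller evaluable number was intended, state it and recompute from it.
5. Say how the table is rounded and apply one rule to both aims. The Aim 2 figures are rounded to the nearest point; rounding up would give 19/17/14.
6. At most, add a note that the Aim 2 figures include no allowance for missing viral loads. If an illustration is wanted, give 20.6/18.3/14.9 for 24% missing, labelled as an assumption.

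The cost is recalculation and wording. No participants are added, and the design and analysis do not change.

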**DATA SHARING AND OWNERSHIP**

During the conduct of the trial, the study database will remain confidential. After study completion, access to data will follow requirements of the Infectious Diseases Institute, National Institutes of Health and the University of Washington. The University of Washington International Clinical Research Center has a Manuscripts and Ancillary Studies Committee established to enable data and specimen

collaborative work from studies conducted through the research group. Intellectual property and data generated under the proposed project will be administered in accordance with Uganda, University of Washington and NIH policies, including the National Guidelines for Research involving Humans as Research Participants (2014) and the NIH Data Sharing Policy and Implementation Guidance of March 5, 2003.

Materials generated under the project will be disseminated in accordance with University/participating institutional and NIH policies. Depending on such policies, materials may be transferred to others under the terms of a material transfer agreement. Access to databases generated under the project will be available for educational, research and non-profit purposes as approved by the relevant IRBs. Publication of data shall occur during the project, if appropriate, or at the end of the project, consistent with normal scientific practices. We will publish our findings in a timely fashion and will present unpublished data at appropriate research conferences. We are committed to collaboration in complex disease research and will participate in data-pooling studies as allowed by our currently established consent forms and IRBs.

Data obtained from this research study are the property of the Infectious Diseases Institute of Makerere University and the University of Washington International Clinical Research Center. Local researchers shall have unrestricted access rights to datasets collected through this collaborative research project in accordance with Uganda guidelines.

## **DISSEMINATION PLAN**

Dissemination of study results will follow principles of good participatory practice. Study results will be disseminated through presentations to study participants, stakeholders and policy makers, and published in conference abstracts and peer-reviewed journals. Participants will be informed that if they so desire, they will be contacted at the end of the study for the purpose of informing them about study results. Trial results will also be shared with the community advisory board, the Ministry of Health, implementing partners and civil society groups with interest in reproductive health.

## **HUMAN SUBJECTS CONSIDERATIONS**

The study protocol, site-specific informed consent forms, participant education and recruitment materials, and other requested documents — and any subsequent modifications — will be reviewed and approved by the IRBs/ECs responsible for oversight of research conducted at the study site. Subsequent to initial review and approval, the responsible IRBs/ECs will review the study at least annually.

### *Informed consent*

Written informed consent will be obtained from each study participant prior to enrollment. Participants will be offered copies of the informed consent forms. The study site will draft informed consent forms that describe the purpose of the study, the procedures to be followed, and the risks and benefits of participation, in accordance with all applicable regulations, based on the consent forms provided in the Appendix. The site will translate the forms into the local language and verify the accuracy of the translation by performing an independent back-translation, which will be reviewed and approved by the International Clinical Research Center at the University of Washington.

### *Risks*

*Confidentiality.* Although the study site will make every effort to protect participant privacy and confidentiality, it is possible that participants' involvement in the study could become known to others, and that social harms may result (i.e., because participants could become known as participating in a trial involving HIV-positive persons). For example, participants could be treated unfairly or discriminated against, or could have problems being accepted by their families and/or communities.

*HIV testing.* Participants may become embarrassed, worried, or anxious when completing their HIV risk

assessment and/or receiving HIV counseling. They also may become worried or anxious while waiting for their (or their partner's) HIV test results. Couples-based counseling and discussions of study participation may raise issues between partners, particularly related to blame (from HIV-negative men) and potential termination of the partnership. Participants who learn that they have HIV may experience anxiety or depression related to their test results. Individual and couples-based HIV counseling will be provided by counselors and clinicians who have been trained in specific issues related to HIV serodiscordant couples, including stigma, blame, methods to avoid transmission, and available support services.

*ART adherence counseling.* Participants may become embarrassed, worried, or anxious when talking about their emotions and/or experiences. The counseling staff, including peer mothers, will be highly trained to protect participant's confidentiality and privacy while minimizing uncomfortable feelings. Participants may also experience more intense psychological discomfort during counseling sessions or data collection due to disclosure about common mental disorders or fears of intimate partner violence. Steps will be taken to minimize any psychological discomfort by providing ongoing counseling during study visits and access to staff by WhatsApp and telephone, as needed. Lists of referrals are in place to address recent psychological problems needing intervention. Participants who disclose suicidal ideation, or a history of suicide attempt, either through their questionnaire responses or in conversations with study staff, will be immediately linked to further medical care.

*Social harm.* Intimate Partner Violence (IPV) following HIV status disclosure is an important consideration for couple studies. In a Kenyan study, women who experienced recent IPV were less likely to report partner self-testing (adjusted relative risk ratio [a RRR] 0.10; 95% CI: 0.02-0.47) or couple testing (a RRR 0.13; 95% CI: 0.03-0.54) (76). Recent partner violence was not significantly associated with male partner self-testing or couple testing. However, couple testing was less likely if the male partner had a neutral or negative reaction to the offer of a self-test (aOR 0.32; 95% CI: 0.12-0.87) or was not easily persuaded to use a self-test (a OR 0.25; 95% CI: 0.09-0.76).

We have extensive experience with counseling >1700 couples over the past decade at the IDI-Kasangati research site. In a study that utilized data from our site, IPV was reported in 2.7% of visits by HIV-positive women and in 2.2% of visits by HIV-negative women (77). In the Partners PrEP Study, HIV-negative women in serodiscordant partnerships reported IPV at 0.7% of study visits (78). Serodiscordant couples perceive PrEP as a solution to the "discordance dilemma" - the desire to avoid HIV acquisition while preserving the relationship. PrEP users benefit from the adherence support of positive partners on ART, and this mutual reinforcement motivates couples who wish to stay together to do so (79).

The majority of women receive support and understanding from their partners when they disclose their HIV status. Fewer than 5% of couples separate or divorce after disclosure of an HIV positive test (80). A study in South Africa found no evidence that inviting male partners to ANC and HTS increased risk of self-reported IPV in women or men when compared to letters inviting male partners for pregnancy information sessions (38). Overall, no association between HIV status and IPV was demonstrated in an analysis of data from Demographic and Health Surveys conducted in Kenya, Liberia, Malawi, Mali, Rwanda, Zambia and Zimbabwe (81).

*Phlebotomy.* Participants may experience discomfort or pain when undergoing phlebotomy. They also may feel dizzy or faint, and/or develop a bruise, swelling, or infection where the needle is inserted.

*PrEP medication.* Risks and side effects related to PrEP occurring in a minority of individuals taking PrEP - gastrointestinal intolerance, such as nausea, diarrhea or vomiting, flatulence; rare but serious - lactic acidosis/ severe hepatomegaly with steatosis, renal impairment, including cases of acute renal failure and Fanconi's syndrome (renal tubular injury with severe hypophosphatemia), increase in bone metabolism leading to osteopenia, hypersensitivity reaction.

*Informal Focus Group Discussions.* The risks of participating in the informal focus group discussions are minimal, and participation is voluntary. It is possible that participants might become tired during the focus group. They may also find some of the questions uncomfortable or hard to answer. Participants can choose to leave the focus group discussion at any point.

